For the secondary outcome, i.e., time to the first stenosis event, we will compare stenosis-free survival of Ticagrelor versus placebo using the Kaplan-Meier method. Survival probabilities and corresponding 95% confidence interval (CI) will be calculated at landmark time points for each arm, and survival difference between the two arms will be evaluated using a one-sided log-rank test stratified by the history of stenosis. Further, a stratified Cox proportional-hazards model will be used to derive the hazard ratio and 95% CI between the two regimens.

6. Have you been working with a statistician in designing this protocol?

Yes

IRB-HSR# 17224: Randomized, Placebo-controlled, Single Blind, Trial to Determine the Safety and Efficacy of Ticagrelor for Maintaining Patency of Arterio-Venous Fistulae Created for Hemodialysis

IF YES, what is their name?

[name]

Biomedical Research

1. What will be done in this protocol?

Subjects will be in this study for 1 year. Up to eighty eight patients with ESRD on chronic HD and a functioning AVF will be enrolled. For statistical purposes we will need to have seventy people complete the study. Consent form will be obtained. History and dialysis parameters will be taken at the screening visit. At the screening visit we will also be collecting a serum sample to perform a pregnancy test on female subjects of child bearing potential. This will be collected in a 3.5ml gold top serum separating tube. Study participants will be on the study medication (Ticagrelor) or placebo for six months (Visit 1 to Visit 12). Subjects will take the study medication twice a day. They will take it once in the morning and once in the evening. We will also instruct them to try and take it around the same times each day if possible. We will be collecting study medication to check for compliance at Visits 3, 6, 9, and 12. There will be a follow up for these subjects for six months (Visit 13 to Visit 18). Subjects will have a physical performed at screening, visit 12 (this is the last visit when subjects are on medicine), and at visit 18 which is the end of the study. We will be looking at hemoglobin levels that are collected as standard of care two times a month. We will be collecting the bleeding time weekly as well. This will be done at all visits (screening to Visit 18) which we define as the time it takes for a subjects' access to stop bleeding.

The following data will be documented on each subject at screening:

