1-Age/gender/race/body weight/cause of ESRD

2-Vintage of HD

3-Time since access was placed

4-Type and place of access and blood flow rate of access

5-History of prior access problems

6-Comorbid conditions (Example: Hypertension, coronary artery disease, Diabetes Mellitus, Bleeding problems, peripheral vascular disease).

7-Current medications (Example: Coumadin, Erythropoiesis stimulating agents, heparin, other antiplatelets, digoxin, statins)

This data will be obtained from the dialysis computer system and will be verified with the subject.

8-Physical Exam

9-Vital signs (blood pressure, heart rate, and weight) will be obtained from the subject's dialysis record.

Adverse events and concomitant medications will be reviewed at each study visit. We will also note any access issues at each study visit.

Study Medication Stopping Rules for Prolonged Bleeding:

If post treatment bleeding time is prolonged more than 30 minutes we will stop the study drug and refer for fistulogram,

If bleeding still persists after fistulogram and intervention we will continue to hold the study drug and do work up for bleeding. We will continue to hold study drug for 5 days if signs of increased tendency for bleeding as recurrent Epistaxis > twice in one week, if any evidence of GI bleed, or if Hgb should drop > 1gm in one week. If the bleeding is believed to be drug related or it no resolution occurs the subject will be withdrawn from the study.

We will also hold study drug for 5 days if hemoglobin is consistently less than 8g/dL for 2 consecutive weeks, or hemoglobin dropping 1g/dL in one week.

IRB-HSR# 17224: Randomized, Placebo-controlled, Single Blind, Trial to Determine the Safety and Efficacy of Ticagrelor for Maintaining Patency of Arterio-Venous Fistulae Created for Hemodialysis

For a prolonged bleeding event standard practice will be applied, including: (prolonged bleeding is defined as bleeding more than 30 minutes)

- **Direct pressure.** Any bleeding that warrants an emergency department visit should be immediately controlled with the application of direct digital pressure to the puncture site for 5-10 minutes. Once the bleeding abates, the patient should be observed for rebleeding or early thrombosis for 1-2 hours.

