- **Gelatin sponges.** Commonly seen in the emergency department as Gelfoam®, this adjunct may aid in the hemostasis of bleeding AV grafts. Although studies or case reports of this material being used in this setting are not found in the medical literature, our clinical practice has demonstrated success by including it in the management of this problem.

Life-Threatening Bleeding From Hemo Access

A vascular surgeon should be emergently consulted if hemorrhage cannot be quickly controlled. An adjunctive suture may be placed if there appears to be a small laceration of the graft rather than a puncture wound. This suture is used only after other measures to control bleeding described above have also failed.

Other life threatening bleeding: Subjects will be sent to the emergency department

2. Will you be using data/specimens in this study that were collected previously, with the use of a research consent form, from another research study?

No

3. List the procedures, in bullet form, that will be done for research as stipulated in this protocol.

- Physical Exams
- Administration of Investigational Drug
- HcG Blood Pregnancy Test
- Collection of Bleeding Time

Note: Laboratory data will be captured and recorded for research purposes from blood collected as part of the subject's clinical care-no additional blood is collected for the purpose of this study.

4. Will any of the procedures listed in item # 2 have the potential to identify an incidental finding?

Yes

► IF YES, check one of the following two options:

X The examination(s) utilize(s) the same techniques, equipment, etc., that would be used if the subject were to have the examination(s) performed for clinical care. There exists the potential for the discovery of clinically significant incidental findings.

- The PI takes full responsibility for the identification of incidental findings:
- The PI will inform the subjects verbally of all incidental findings that are of clinical significance or are of questionable significance.
- A follow-up letter describing the finding should be provided to the subject with instructions to either show the letter to their PC or if the subject has no PCP, the subject should be instructed to make an appointment at UVa or at the Free Clinic.

IRB-HSR# 17224: Randomized, Placebo-controlled, Single Blind, Trial to Determine the Safety and Efficacy of Ticagrelor for Maintaining Patency of Arterio-Venous Fistulae Created for Hemodialysis

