- Weekly Hemoglobin Tests

2.3 Under what criteria would an INDIVIDUAL SUBJECT’S study treatment or study participation be stopped or modified

At subject, PI or sponsor’s request

Treatment would be stopped if the subject had a serious adverse event deemed related to study

Subjects will be stopped if they meet one or more of the study stopping rules

2.4 Under what criteria would THE ENTIRE STUDY need to be stopped.

IRB-HSR# 17224: Randomized, Placebo-controlled, Single Blind, Trial to Determine the Safety and Efficacy of Ticagrelor for Maintaining Patency of Arterio-Venous Fistulae Created for Hemodialysis

*These are called stopping rules for early termination of the entire study.
List criteria regardless of whether the study is sponsored or not.
Be sure to include any criteria for which the UVa PI would halt the study at UVa.*

Per IRB, PI, DSMB, or sponsor discretion

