5.1. Who is responsible for overseeing safety data for this study ?

- No additional oversight body other than PI at UVa Skip question 5.2

5.2. What is the composition of the reviewing body and how is it affiliated with the sponsor? N/A

5.3. What items will be included in the aggregate review conducted by the PI?

- All adverse events
- Unanticipated Problems
- Protocol violations
- Audit results
- Application of dose finding escalation/de-escalation rules

These should be outlined under 2.4.
- Application of study designed stopping/decision rules
- Early withdrawals
- Whether the study accrual pattern warrants continuation/action
- Endpoint data

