5.4 How often will aggregate review occur?

For additional information on aggregate review see:
www.virginia.edu/vpr/irb/hsr/continuations.html#aggreview

- Annually

5.5. How often will a report, regarding the outcome of the review by the DSMB/DSMC, be sent to the UVa PI?

IRB-HSR# 17224: Randomized, Placebo-controlled, Single Blind, Trial to Determine the Safety and Efficacy of Ticagrelor for Maintaining Patency of Arterio-Venous Fistulae Created for Hemodialysis

A copy of these reports must be sent to the IRB if applicable as soon as they are received by the PI. Do not wait until the next continuation to submit them to the IRB.

NA- PI is the overall person overseeing the safety data for this study.

5.6. How will a report of the information discussed in question 5.4 OR 5.5 be submitted to the IRB?

Part of IRB-HSR continuation status form

Payment

What is the difference between compensation and reimbursement?

A reimbursement is used when the subject is paid back for travel expenses such as mileage, lodging, food while traveling. Receipts or mileage must be submitted for a reimbursement.

Compensation is "payment" for things such as time, discomfort, inconvenience.

Total possible compensation should reflect the true value of the total possible dollar amount per participant for one year involvement in the study whether it be cash, check, gift card, goods, etc. or a combination of these items.

Retention "Gifts"- gifts may be given to a subject periodically during the study to remind them they are in the study. Sponsors may provide such items as water bottles, birthday cards etc. to the subject. NOTE: Cash or gift cards are NOT allowed as retention items.

1. Are subjects being reimbursed for travel expenses (receipts /mileage required)?No

2. Are subjects compensated for being in this study?

Yes

2a. What is the maximum TOTAL compensation to be given over the duration of the protocol?

\$415.00

2b. Explain compensation to be given.

- For the screening visit subjects will be compensated \$25.00 due to length of time necessary to complete this visit.
- For the first 6 months of study participation, when subjects are on ticagrelor or placebo (visit 1 to visit 12) subjects will be compensated \$25.00 for their time in completing these visits.
- For the last 6 months of study participation, when study subjects will **not** be taking ticagrelor or placebo subjects will be compensated \$15.00 for their time in completing these visits.

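### The one-week hemoglobin-drop hold rule depends on a monitoring schedule that the protocol states two ways, weekly and twice monthly

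*Combined protocol and SAP*

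**What the plan says.** All references are to the combined protocol and SAP.

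- **Hold rule.** Under Study Medication Stopping Rules for Prolonged Bleeding, drug is held for 5 days if "hemoglobin is consistently less than 8g/dL for 2 consecutive weeks, or hemoglobin dropping 1g/dL in one week". The preceding paragraph of that section gives the drop limit as a strict inequality: "if Hgb should drop > 1gm in one week".
- **Schedule A.** Biomedical Research, item 1: "We will be looking at hemoglobin levels that are collected as standard of care two times a month".
- **No research draw to fill a gap.** The note under Biomedical Research, item 3, says that laboratory data come from blood taken for clinical care and that "no additional blood is collected for the purpose of this study". The one blood sample listed for research is the screening pregnancy test.
- **Schedule B.** Data and Safety Monitoring Plan (DSMP) 2.2 lists, among the measures that reduce risk, "Weekly Hemoglobin Tests".
- **Visits and dosing.** Subjects take drug for 6 months and are seen twice a month in that time, at Visits 1 to 12.

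**The concern.** A rule about a fall within one week can be applied only if two values about a week apart exist and someone compares them in time. One of the two stated schedules does not supply such pairs, and the protocol does not say which governs. The paragraph holding schedule A does not help: it calls bleeding time weekly, then says that it is done at all visits, and on-drug visits are twice a month.

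Safety is the primary objective, the protocol says that the drug was never tested in end-stage renal disease, and it names an increased risk of severe bleeding. Hemoglobin is the objective measure behind two hold triggers. If the schedule is unclear, so is what those triggers did. A small number of hemoglobin holds could mean few falls, or falls that the draws could not show.

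**Working it through.** The protocol gives no figure on this point to reproduce, so the check is schedule arithmetic.

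**Inputs.** Dosing of 6 months, taken as 365.25/2 = 182.6 days; 12 values on the twice-monthly schedule; a 7-day window and a 1 g/dL limit from the stopping rules. Even spacing is an assumption, because the protocol does not state the spacing.

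**1. Twice-monthly values, evenly spaced.**
- Gap = 182.6/12 = 15.2 days (14.0 to 15.5 days for months of 28 to 31 days).
- This is 15.2/7 = 2.2 times the rule's window, so no scheduled pair is a week apart.
- A 1 g/dL fall between such values averages 7/15.2 = 0.46 g/dL per week. The two values cannot tell a gradual fall from one that took place within a week.
- The low trigger rests on two values 15.2 days apart with none between.
- If the two monthly draws fell in adjacent weeks, one week per month would be covered and about 30.4 - 7 = 23.4 days would not.

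**2. Weekly values, looked at twice a month.** Time from the fall to its being seen:
- Looks at every second draw: uniform over 14 days, mean 7.0, maximum 14.
- Looks not synchronised with draws: mean 7/2 + 15.2/2 = 3.5 + 7.6 = 11.1 days; maximum 7 + 15.2 = 22.2 days.

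**3. Weekly values, checked weekly.** There are 182.6/7 = about 26 values, and every one-week change can be assessed. Time to being seen: mean 3.5 days, maximum 7.

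**4. Chance holds.** Suppose true hemoglobin is stable and values vary independently and normally around it with standard deviation SD. The expected number of falls of at least L between neighbouring values is (number of gaps) × Φ(-L/(SD√2)). The protocol gives no SD, so 0.3 to 0.7 g/dL is assumed, with L = 1 g/dL.

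| SD (g/dL) | Φ(-1/(SD√2)) | Twice monthly, 11 gaps | Weekly, 25 gaps |
|---|---|---|---|
| 0.3 | 0.0092 | 0.10 | 0.23 |
| 0.5 | 0.0786 | 0.87 | 2.0 |
| 0.7 | 0.156 | 1.72 | 3.9 |

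The twice-monthly column applies only if the trigger is redefined as a fall between consecutive available values. At 5 days per hold, the largest entry is 3.9 × 5 = about 20 of 183 drug days.

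**The case against.** The strongest reply is that this is a matter of clarification. The stopping rules count in weeks and DSMP 2.2 lists weekly tests; both fit weekly clinical draws, which need no extra study blood. In Biomedical Research item 1, the twice-monthly phrase can describe how often the team looks, matching the visits, rather than how often blood is drawn. On that reading the rule is late, not unusable. Unscheduled clinical values could also trigger it, and the bleeding-time, nosebleed and gastrointestinal-bleed triggers do not depend on hemoglobin.

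Most of this stands. A reader might infer that the drop rule simply cannot be run, but the documents do not support that. It would require that item 1 overrides DSMP 2.2, that draws are evenly spaced, and that no other values exist. Nor do they show that staff would treat patients differently: drug is dispensed in one dialysis unit, and nothing says that draw frequency varies by patient. What survives is that two schedules are written down, and the rule works as written only if weekly values are checked weekly.

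A reader might also infer that annual aggregate review leaves 6 months of dosing without effective oversight, since DSMP 5.1 provides "No additional oversight body other than PI at UVa". The documents do not support this as an error. Investigators are unblinded (Statistical Considerations, item 1). DSMP 2.4 lets the principal investigator (PI), among others, stop the whole study at their discretion. Adverse events are reviewed at every visit, and serious events not needing expedited reporting go to the drug supplier quarterly.

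Nor is the share of drug-time elapsed at a first annual review fixed, because the clock start and actual accrual are not stated. With 88 patients at 12 per month and the clock at first entry, 16 patients remain on drug at month 12 with on average 0.67 months left, so 1 - (16 × 0.67)/(88 × 6) = 98% has elapsed. With the 43 enrolled patients spread evenly over an assumed 24 months and the clock starting 3 months before first entry, it is (3/24 × 6 + 6/24 × 3)/6 = 25%.

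**Conclusion.** The point holds as an internal contradiction in a safety rule of a trial whose primary objective is safety. Its size depends on which schedule was meant:

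- **Twice-monthly draws, evenly spaced:** the one-week drop trigger cannot be assessed on scheduled values, and the low trigger rests on values about 15 days apart.
- **Weekly draws, looked at twice a month:** the drop trigger runs, but a fall is seen on average about 7 to 11 days after it happens (maximum 14 to 22), against 3.5 (maximum 7) with weekly checks.
- **Weekly draws, checked weekly:** the rule works, and Biomedical Research item 1 is the text to correct.

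The two statements of the drop limit also disagree for a fall of exactly 1 g/dL. The wording should be corrected, but nothing here bears on the planned chi-square or log-rank tests. More frequent PI aggregate review would be a preference for timeliness, not the repair of an error.

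**What to change.** 1. **State one hemoglobin schedule.** Where weekly clinical values exist, say that they are captured and checked weekly while on drug, and correct Biomedical Research item 1. Otherwise correct DSMP 2.2 and have the investigator restate both hemoglobin triggers in terms of the values actually available.
2. **Use one drop limit throughout,** either more than 1 g/dL or at least 1 g/dL.
3. **If dosing is already over,** report which schedule was followed and the number of holds under each rule, by arm.
4. **Optional:** hold the PI's aggregate review more often during dosing. DSMP 5.3 already includes "Application of study designed stopping/decision rules" among its items. The same person would review, so this adds timeliness and not independence.

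**Cost.** Items 1 and 2 are wording changes and need no extra blood. Weekly checking adds staff time and, on the assumed SDs, about 0.2 to 3.9 chance 5-day holds per patient. A rule on consecutive twice-monthly values gives about 0.1 to 1.7, but it is a clinical change: it acts on an average fall of 0.46 g/dL per week, less than half the stated rate. The investigator should choose the limit with both sets of figures in view.

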1.1 How will you define adverse events (AE) for this study?

X An adverse event will be considered any undesirable sign, symptom or medical or psychological condition **even if the event is not considered to be related** to the investigational drug/device/intervention. Medical condition/diseases present before starting the investigational drug/intervention will be considered adverse events only if they worsen after starting study treatment/intervention. An adverse event is also any undesirable and unintended effect of research occurring in human subjects as a result of the collection of identifiable private information under the research. Adverse events also include any problems associated with the use of an investigational device that adversely affects the rights, safety or welfare of subjects.

1.2 How will you define serious adverse events?

X A serious adverse event will be considered any undesirable sign, symptom, or medical condition which is fatal, is life-threatening, requires or prolongs inpatient hospitalization, results in persistent or significant disability/incapacity, constitutes a congenital anomaly or birth defect, is medically significant and which the investigator regards as serious based on appropriate medical judgment. An important medical event is any AE that may not result in death, be life-threatening, or require hospitalization but may be considered an SAE when, based upon appropriate medical judgment, it may jeopardize the patient and may require medical or surgical intervention to prevent one of the outcomes listed in the definitions of SAEs.

1.3 What is the definition of an unanticipated problem?

Do not change this answer

An unanticipated problem is any event, experience that meets ALL 3 criteria below:

- Is unexpected in terms of nature, severity or frequency given the research procedures that are described in the protocol-related documents AND in the characteristics of the subject population being studied
- Related or possibly related to participation in research. This means that there is a reasonable possibility that the incident may have been caused by the procedures involved in the research study.

IRB-HSR# 17224: Randomized, Placebo-controlled, Single Blind, Trial to Determine the Safety and Efficacy of Ticagrelor for Maintaining Patency of Arterio-Venous Fistulae Created for Hemodialysis

- The incident suggests that the research placed the subject or others at greater risk of harm than was previously known or recognized OR results in actual harm to the subject or others

1.4 What is the definition of a protocol violation?

Do not change this answer

A protocol violation is defined as any change, deviation, or departure from the study design or procedures of a research project that is NOT approved by the IRB-HSR prior to its initiation or implementation, OR deviation from standard operating procedures, Good Clinical Practices (GCPs), federal, state or local regulations. Protocol violations may or may not be under the control of the study team or UVa staff. These protocol violations may be major or minor violations.

Additional Information: see the IRB-HSR website at

http://www.virginia.edu/vpr/irb/HSR_docs/Forms/Protocol_Violations_%20Enrollment_Exceptions_Instructions.doc

1.5 If pregnancy occurs how will this information be managed?

Adverse Event- will follow adverse event recording and reporting procedures outlined in section 3.

Unanticipated Problems- will follow Unanticipated Problem recording and reporting procedures outlined in section 3.

1.6 What is the definition of a Protocol Enrollment Exception?

NA- No outside sponsor

1.7 What is the definition of a data breach?

Do not change this answer

A data breach is defined in the HITECH Act (43 USC 17932) as an unauthorized acquisition, access, or use of protected health information (PHI) that compromises the security or privacy of such information.

Additional Information may be found on the IRB-HSR Website: [Data Breach](#)

2. Identified risks and plans to minimize risk

2.1 What are identified risks and plans to minimize risk

****Please Also Refer to the Investigator Brochure and the Package Insert for Brilinta/ Ticagrelor**

Adverse Events with Brilinta/Ticagrelor

Frequent complaints (seen in at least 3% of study participants) that have been reported during studies:

- Bleeding
- Dyspnea (Shortness of Breath)
- Cough
- Dizziness
- Nausea
- Atrial Fibrillation (Heart Rhythm Disorder)
- Hypertension (High Blood Pressure)
- Non-Cardiac Chest Pain

IRB-HSR# 17224: Randomized, Placebo-controlled, Single Blind, Trial to Determine the Safety and Efficacy of Ticagrelor for Maintaining Patency of Arterio-Venous Fistulae Created for Hemodialysis

- Diarrhea
- Back Pain
- Hypotension (Low Blood Pressure)
- Fatigue
- Chest Pain
- Headache

More Frequent complaints (seen in at least 6 to 7% of study participants) that have been reported during studies:

- Bradycardia (Slow Heart Rate)
- Elevated Serum Creatinine

There have also been cases of increased uric acid levels for subjects taking ticagrelor. A high uric acid level, or hyperuricemia, is an excess of uric acid in your blood. Uric acid is produced during the breakdown of purine, a substance found in many foods. Once produced, uric acid is carried in your blood and passes through your kidneys, where most of it leaves your body when you urinate. A high uric acid level may result in attacks of gout, but not everyone who has high uric acid gets gout, and not everyone with gout has high uric acid. Increased uric acid may also increase the chances of kidney stones. There is also an increased risk of severe bleeding for subjects taking ticagrelor. Due to the increase risk of severe bleeding there may be a risk of delay in any surgery that you may need while taking this study medication.

Expected Risks related to study participation.	Frequency
Reproductive Risks These are unknown at this time.	Minimized due to the requirements of this protocol.
Violation of subject’s privacy and confidentiality	Minimized due to the requirements of the privacy plan in this protocol

2.2 List by bullet format a summary of safety tests/procedures/observations to be performed that will minimize risks to participants:

- Study personnel will be checking on patients twice a month for six months while subjects are on study treatment and once a month while subjects are in the follow up visits.
- We will be monitoring the time it takes for the subject’s access to clot.
- AE monitoring at each visit
- Weekly Hemoglobin Tests

2.3 Under what criteria would an INDIVIDUAL SUBJECT’S study treatment or study participation be stopped or modified

At subject, PI or sponsor’s request

Treatment would be stopped if the subject had a serious adverse event deemed related to study

Subjects will be stopped if they meet one or more of the study stopping rules

2.4 Under what criteria would THE ENTIRE STUDY need to be stopped.

IRB-HSR# 17224: Randomized, Placebo-controlled, Single Blind, Trial to Determine the Safety and Efficacy of Ticagrelor for Maintaining Patency of Arterio-Venous Fistulae Created for Hemodialysis

*These are called stopping rules for early termination of the entire study.
List criteria regardless of whether the study is sponsored or not.
Be sure to include any criteria for which the UVa PI would halt the study at UVa.*

Per IRB, PI, DSMB, or sponsor discretion

